The number and percentage of participants without increase of bone age (Greulich and Pyle method)/chronological age ratio from Baseline to Months 6 and 12 will be presented and its two-sided 95% CI will be presented and calculated using the same method as primary efficacy endpoint.

- Change in difference between BA and CA and ratio BA:CA at Months 6 and 12 compared to baseline:

A summary table for the difference between BA and CA and ratio BA:CA will be provided with descriptive statistics (n, mean, SD, median, minimum and maximum) at Baseline, Month 6 and Month 12 and for absolute changes from Baseline.

- Proportion of children who achieve stabilisation of sexual maturation compared to baseline stage using Tanner method at Months 6 and 12:

The number and percentage of participants with no increase in Tanner puberty staging from Baseline to Months 6 and 12 will be presented and its two-sided 95% CI will be presented and calculated using the same method as primary efficacy endpoint.

- Proportion of girls with regression of uterine length at Months 6 and 12 (transabdominal ultrasound):

The number and percentage of girls with regression of uterine length at Months 6 and 12 will be presented and its two-sided 95% CI will be presented and calculated using the same method as primary efficacy endpoint.

- Proportion of boys with absence of progression of testis volumes at Month 6 and 12 (clinical assessment with orchidometer):

The number and percentage of boys with absence of progression of testis volumes at Months 6 and 12 will be presented and its two-sided 95% CI will be presented and calculated using the same method as primary efficacy endpoint.

- Change in body weight and BMI at Month 6 and 12:

A summary table for the body weight and BMI will be provided with descriptive statistics (n, mean, SD, median, minimum and maximum) at Baseline and Months 6 and 12 and for absolute changes from Baseline.

9.4.3.1 *Pharmacokinetic Analyses*

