5.7.3 Analysis of Secondary Efficacy Endpoints

5.7.3.1 Endpoint

Secondary efficacy endpoints and evaluations are summarised in following table:

Table 1 Secondary Efficacy Endpoints and Evaluations

| Measure | Timepoint | Variable | Endpoint |
|--|--|--|---|
| Peak LH after GnRH stimulation test | Month 3 and Month 12 | LH suppression (stimulated peak LH ≤ 5 IU/L after GnRH stimulation) | 
 Proportion of children with LH suppression defined as stimulated peak LH ≤ 5 IU/L after GnRH stimulation at Month 3 and 12 |
| | Month 6 and Month 12 | | 
 Proportion of children maintaining LH suppression defined as stimulated peak LH ≤ 5 IU/L after GnRH stimulation from Month 6 to 12 |
| Basal LH and FSH | Baseline, Month 3, Month 6, Month 9 and Month 12 | LH and FSH concentration | Change in basal serum LH and FSH levels at Months 3, 6, 9 and 12 compared to baseline |
| Peak LH and FSH after GnRH stimulation test | Baseline, Month 3, Month 6 and Month 12 | LH and FSH concentration | Change in peak serum LH and FSH levels at Months 3, 6 and 12 compared to baseline |
| Pre-pubertal levels of sex steroids | Month 3, Month 6, Month 9 and Month 12 | oestradiol ≤ 20 pg/mL [<73 pmol/L] in girls or testosterone ≤ 30 ng/dL [<0.8 nmol/L] in boys | 
 Proportion of children with pre-pubertal levels of sex steroids (defined as oestradiol ≤ 20 pg/mL in girls or testosterone ≤ 30 ng/dL in boys) at Months 3, 6, 9 and 12 |
| | Baseline, Month 3, Month 6, Month 9 and Month 12 | | 
 Change in sex steroids levels at Months 3, 6, 9 and 12 compared to baseline |
| Height (Z-score and percentile for height for age) and growth velocity | Baseline, Month 6, and Month 12 | Height (Z-score and percentile for height for age) and growth velocity | 
 Change in height (Z-score [height for age] and percentile for height for age) and growth velocity at Months 6 and 12 Height absolute Z-scores and percentiles at Baseline, Months 6, and 12 Change in Height at Months 6, and 12 compared to baseline |

| | | | |
|--|--|---|---|
| BA (Greulich and Pyle method):CA ratio | Month 6 and Month 12 | BA and CA | Proportion of children in whom the BA (Greulich and Pyle method):CA ratio did not rise at Months 6 and 12 relative to baseline (X-ray) |

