| BA and CA and ratio BA:CA | Baseline, Month 6 and Month 12 | BA and CA | Change in difference between BA and CA and ratio BA:CA and BA at Months 6 and 12 compared to baseline |
| Stabilisation of sexual maturation | Month 6 and Month 12 | Children who achieve stabilisation of sexual maturation | Proportion of children who achieve stabilisation of sexual maturation at Month 6 and 12 compared to baseline stage using Tanner method |
| Girls uterine length | Month 6 and Month 12 Baseline, Month 6 and Month 12 | Uterine length | 
 Proportion of girls with regression of uterine length (transabdominal ultrasound) at Months 6 and 12 Change in uterine length at Months 6 and 12 compared to baseline |
| Boys testis volumes | Month 6 and Month 12 Baseline, Month 6 and Month 12 | Testis volumes | 
 Proportion of boys with absence of progression of testis volumes (clinical assessment with orchidometer) at Months 6 and 12 Change in testis volumes at Months 6 and 12 compared to baseline |
| Body weight and BMI | Month 6 and 12 | Body weight and BMI | Change in body weight and BMI at Months 6 and 12 compared to baseline |

The SAS code and algorithm of Z-score and percentile for height for age are presented in Appendix (A5).

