5.7.3.2 Secondary Analysis

For secondary efficacy endpoints related to a change at Months 3, 6, 9 and 12 compared to baseline, the descriptive summary statistics (n, mean, SD, median, minimum, maximum) will be calculated on the ITT. Exact two-sided 95% CIs will also be constructed for all secondary endpoints expressed as percentages.

GV cm/y, Height, Weight, BMI, FSH, LH values, Bone age, difference between Chronological age and Bone age, Oestradiol/Testosterone, Uterine Length and Testicular Volume over time will be graphically presented via individual observed values (scatter) as well as mean and

standard deviation of the observed values (Baseline, Month 3, Month 6, Month 9 and Month 12).

5.7.3.3 *Sensitivity Analysis*

No sensitivity analysis will be performed.

5.7.3.4 *Subgroup Analysis*

No subgroup analyses will be performed.

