7 DERIVED DATA (IF APPLICABLE)

When applicable, below derivation rules should be followed:

- Change from baseline**

Change from baseline at a given visit will be calculated as a difference from baseline.

- Chronological Age**

Chronological Age (years) will be calculated as follows and keep two decimals for the calculated result:

Chronological Age = (Visit Date - birth date + 1)/365.25.

- **BMI**

BMI (kg/m²) will be derived as Weight (kg)/[Height(cm)/100]^{**2} measured at each visit and rounded to the nearest decimal.

- **Bone Age**

For bone age recorded as m+, n- or m-n, the original result will be listed in listing. And for m+, we will use m+0.25 in the summary analysis, for n-, we will use n-0.25 in the summary analysis, for m-n, we will use middle point between m and n in the summary analysis. For examples, 9+ will be updated to 9.25, 8- will be updated to 7.75 and 9-10 will be updated to 9.5. There is one exception, 8.8+ will be updated to 8.825 in the summary analysis.

- **Growth Velocity**

For growth velocity recorded as m-n, the original result will be listed in listing and we will take the middle point between m and n in the summary analysis. For example, 7-8, will be updated to 7.5 in the summary analysis.

- **Oestradiol and Testosterone**

For oestradiol and testosterone recorded as <17.936 or <11.981, the original result will be listed in listing and update <17.936 to 17.936, <11.981 to 11.981 in the summary analysis.

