where the L, M, and S are the values from the appropriate table corresponding to the age in months of the child (** indicates an exponent, such that $M(1+LSZ)^{**}(1/L)$ means raising $(1+LSZ)$ to the $(1/L)$ th power and then multiplying the M; $\exp(X)$ is the exponentiation function, e to the power X). Z is the z-score that corresponds to the percentile. z-scores correspond exactly to percentiles, e.g., z-scores of -1.881, -1.645, -1.282, -0.674, 0, 0.674, 1.036, 1.282, 1.645, and 1.881 correspond to the 3rd, 5th, 10th, 25th, 50th, 75th, 85th, 90th, 95th, and 97th percentiles, respectively.

The LMS parameters need to be adjusted based on actual age (age), use the following equation:

```
ageint = CDCref_d._agemos2- CDCref_d._agemos1;
dage= age - CDCref_d._agemos1;
L=CDCref_d._LLG1+ (dage*(CDCref_d._LLG2- CDCref_d._LLG1))/ageint;
M=CDCref_d._MLG1+ (dage*(CDCref_d._MLG2- CDCref_d._MLG1))/ageint;
S=CDCref_d._SLG1+ (dage*(CDCref_d._SLG2- CDCref_d._SLG1))/ageint;
```

To obtain the z-score (Z) and corresponding percentile for a given measurement (X), use the following equation:

$$Z = \frac{((X/M)^{**}L) - 1}{LS}, L \neq 0$$

or

$$Z = \ln(X/M)/S, L=0$$

where X is the physical measurement (e.g. weight, length, head circumference, stature or calculated BMI value) and L, M and S are the values from the appropriate table corresponding to the age in months of the child (or length/stature). $(X/M)^{**}L$ means raising the quantity (X/M) to the Lth power.

For example, to obtain the 5th percentile of height-for-age for a 9-month-old male, we would look up the L, M and S values from the CDCref_d table, which are _LLG1=-1.29571459, _MLG1=70.94803912, _SLG1=0.038546833, _LLG2=-1.177919048, _MLG2=72.34586111, _SLG2=0.038526262.

After adjustment by age, L, M, S would be -1.236816819, 71.646950115, and 0.0385365475, respectively. Using the equation above, we calculate that the z-score for this child is 1.15. This z-score corresponds to the 88th percentile.

CCI

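### Body weight and BMI are summarised only on the raw scale in growing children with no control arm, so the summaries cannot show whether gain was more or less than expected for age and sex; add weight-for-age and BMI-for-age z-scores.

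*Protocol*

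**What the plan says.** Protocol section 3 and SAP 2.1.2 list change in body weight and BMI at Months 6 and 12 among the secondary objectives. The planned analysis is as follows.

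- Protocol 9.4.3: "A summary table for the body weight and BMI will be provided with descriptive statistics", reported "at Baseline and Months 6 and 12 and for absolute changes from Baseline".
- SAP 5.7.3.1, Table 1: "Change in body weight and BMI at Months 6 and 12 compared to baseline".
- SAP section 7: "Change from baseline at a given visit will be calculated as a difference from baseline". BMI is weight over height squared, "measured at each visit and rounded to the nearest decimal".
- SAP 5.7.3.2: individual observed values, means and SDs are plotted over time for a list that begins "GV cm/y, Height, Weight, BMI, FSH, LH values, Bone age".

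Tables are shown for Female, Male and Overall (SAP 5.1.1). No z-score, percentile or other age-referenced measure of weight or BMI appears in the readable text.

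Height is treated differently. Protocol 9.4.3 and SAP Table 1 plan change in height-for-age z-score and percentile, and the SAP also lists "Height absolute Z-scores and percentiles at Baseline, Months 6, and 12". SAP Appendix A5 gives the LMS equation for this, "where X is the physical measurement (e.g. weight, length, head circumference, stature or calculated BMI value".

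Protocol 4.2 describes the study as uncontrolled. Protocol 5.1 limits entry to girls under 9 and boys under 10.

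**The concern.** Children of this age gain weight as they grow, whether or not a drug affects weight. A controlled trial removes that background by comparing arms. This trial has one arm, so the only available yardstick is an external growth reference. The plan uses one for height but not for weight or BMI.

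The stake is interpretation. A positive mean change in kilograms could be greater than, equal to or less than what children of that age and sex would be expected to gain, and the planned tables do not distinguish these cases. A given change in kilograms also need not mean the same at different ages, and the tables do not standardise for age.

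**Working it through.** **1. Weight and BMI beside height, same children, same visits**

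| | Weight, BMI | Height |
|---|---|---|
| Values at baseline, Months 6 and 12 | raw | z-score and percentile |
| Change from baseline | raw difference | z-score, percentile and raw |
| Plots | observed values | observed values |
| Referenced to age and sex | no | yes |

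**2. Reproducing the SAP's LMS figures.** The documents state no number for weight or BMI, so the check uses the worked example in A5 (length of a 9-month-old boy). At age 9 in the interval 8.5 to 9.5 months, the interpolation weight is (9 − 8.5)/1 = 0.5.

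- L = (−1.29571 − 1.17792)/2 = −1.2368
- M = (70.9480 + 72.3459)/2 = 71.6470
- S = (0.038547 + 0.038526)/2 = 0.03854

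All three match the SAP. A z-score of 1.15 corresponds to the 87.5th percentile, against the SAP's rounded 88th.

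**3. What the raw scale does under reference growth.** Use X = M(1 + LSZ)^(1/L) at both ends of that one-month interval, holding Z fixed.

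| Z | X at start | X at end | Raw change | z change |
|---|---|---|---|---|
| −2 | 65.92 | 67.20 | +1.28 | 0 |
| 0 | 70.95 | 72.35 | +1.40 | 0 |
| +2 | 76.95 | 78.43 | +1.48 | 0 |

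A child growing exactly along the reference shows a raw change at every Z and a z-score change of zero. This shows the mechanism only: the example is infant length, not weight or BMI at the trial's ages.

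**4. How readily growth alone gives a positive mean (assumed inputs).** Let r be mean growth divided by the SD of individual raw changes, and let the drug effect be zero. The probability that a 95% interval for the mean change lies wholly above zero is about Φ(r√n − 1.96). With n = 62, √62 = 7.874:

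- r = 0.25: Φ(0.01) = 50%
- r = 0.5: Φ(1.98) = 98%
- r = 1.0: Φ(5.91) > 99.9%

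These ratios are assumptions. The plan specifies no interval for these means; the calculation only shows how little growth is needed for a clearly positive average.

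**5. The ambiguity in kilograms (assumed inputs).** Day 1 to Day 337 is 336 days, and 336/365.25 = 0.92 year. Suppose ordinary gain is 2 to 4 kg and 0.2 to 0.7 kg/m² a year; neither range is in the documents. Expected gain is then 0.92 × 2 = 1.8 to 0.92 × 4 = 3.7 kg, and about 0.2 to 0.6 kg/m². A hypothetical observed mean of +3 kg would lie between 1.2 kg above and 0.7 kg below expectation. For BMI the interval can be longer, because the schedule places auxological measurements at Screening and not on Day 1: from Day −28 to Day 344 is 28 + 343 = 371 days, or 1.02 years, giving about 0.2 to 0.7 kg/m².

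**6. Effect on the rest of the design.** None. The exact binomial plan still gives 56 or more responders out of 62, one-sided alpha 0.0238 and power 0.858, and 62/0.95 = 65.3, rounded up to 66, as stated.

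**The case against.** **The objective is descriptive and is met as planned.** It asks for an assessment of change, with no test, threshold or success rule, and the tables supply that. This stands. A reader might infer that the objective cannot be answered at all; the documents do not support that. It can be answered, but the answer is hard to interpret.

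**Z-scores would not isolate the drug.** They subtract the growth of a reference population of the same chronological age. These children have bone age more than one year ahead of chronological age (Protocol 5.1) and a disease that accelerates growth (Protocol 2.2), so their z-score path without treatment need not be flat. This also stands. A reader might infer that z-scores would separate treatment effect from everything else; without a control arm they cannot.

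**A5 is a height appendix.** Its interpolation uses only height parameters. The list in "where X is the physical measurement (e.g. weight, length, head circumference, stature or calculated BMI value" is a general definition of X that also names head circumference, which is not a planned measurement here. This stands in part: the equation applies to weight and BMI, but their parameters are not specified.

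**There are mitigations.** Values as well as changes are tabulated, results are shown by sex, BMI already scales weight for height, listings carry age and gender, and SAP section 1 permits exploratory analyses. No data would be lost. However, none of the planned summaries is referenced to age, and an analysis added later would have to be identified as post hoc.

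**Conclusion.** The point holds as a modest, inexpensive improvement to a descriptive secondary endpoint. Weight and BMI are reported only on the raw scale, in growing children without a comparator, so the planned output cannot say whether gain was more or less than expected for age and sex. The plan already applies the remedy to height.

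The size of the problem cannot be fixed from the documents, which contain no weight or BMI reference values for these ages. The probabilities and kilogram ranges above depend wholly on the stated assumptions; the conclusion does not, since it needs only that some growth occurs over about a year. Parts of the SAP appendices, including text after A5, are blacked out and cannot be checked, but the listed endpoints contain no weight or BMI z-score.

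**What to change.** - In SAP Table 1, and in Protocol 9.4.3 at the next amendment, add change from baseline in weight-for-age and BMI-for-age z-score and percentile at Months 6 and 12. Keep the raw summaries and plots. Record the addition in SAP 2.6, which currently reports no change from the protocol.
- Extend A5 with the weight and BMI parameters. Use one growth reference that covers both measures and is reconciled with the one used for height: Protocol 8.1.5 cites Tanner tables, while SAP A5 uses a US CDC file. The title of the cited Tanner reference names height and weight but not BMI.
- State in the SAP that a z-score change is relative to a reference population of the same chronological age and, without a control arm, does not by itself separate a drug effect from the course of the disease.

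The cost is a small amount of programming, the choice of a reference and a minor text change; the protocol wording can wait for an amendment made for other reasons, since amendments need approval. Weight, height, sex and age are already collected, so no visit or procedure is added.

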9.4.5 Subgroups Analyses

No subgroup analysis will be performed.

9.4.6 Other Analyses

Not applicable

9.5 Interim Analyses

No interim analysis will be performed. If an unplanned interim analysis is deemed necessary, the appropriate sponsor medical director, or designee, will be consulted to determine whether it is necessary to amend the protocol.

10 SUPPORTING DOCUMENTATION AND OPERATIONAL CONSIDERATIONS

10.1 Appendix 1: Regulatory, Ethical, and Study Oversight Considerations

10.1.1 *Regulatory and Ethical Considerations*

- This study will be conducted in accordance with the protocol and with the following:
 - Consensus ethical principles derived from international guidelines including the Declaration of Helsinki and Council for International Organisations of Medical Sciences (CIOMS) International Ethical Guidelines
 - Applicable International Council for Harmonisation (ICH) of Technical Requirements for Pharmaceuticals for Human Use Good Clinical Practice (GCP) Guidelines
 - Applicable laws and regulations
- The protocol, protocol amendments, ICF, IB, and other relevant documents (e.g. any participant recruitment materials) must be approved by the IRB/IEC before the study is initiated.
- Any amendments to the protocol will require IRB/IEC approval before implementation of changes made to the study design, except for changes necessary to eliminate an immediate hazard to study participants.
- The protocol and any substantial amendments to the protocol will require health authority approval prior to initiation except for changes necessary to eliminate an immediate hazard to study participants.
- The investigator will be responsible for the following:
 - Providing written summaries of the status of the study to the IRB/IEC annually or more frequently in accordance with the requirements, policies, and procedures established by the IRB/IEC
 - Notifying the IRB/IEC of SAEs or other significant safety findings as required by IRB/IEC procedures
 - Providing oversight of the conduct of the study at the site and adherence to applicable local regulations, ICH guidelines and the IRB/IEC requirements/procedures.
- The investigator will be responsible for reporting cases of suspected child abuse and/or neglect according to local regulations including local medical association (e.g., American Academy of Pediatrics, EU Academy of Pediatrics) or Health Department guidelines.

10.1.2 *Financial Disclosure*

Investigators and sub-investigators will provide the sponsor with sufficient, accurate financial information as requested to allow the sponsor to submit complete and accurate financial certification or disclosure statements to the appropriate regulatory authorities. Investigators are responsible for providing information on financial interests during the course of the study and for one year after completion of the study.

10.1.3 *Legal Guardian Consent and Paediatric Participant Assent Processes:*

- The informed consent/assent and any participant recruitment materials must be in compliance with ICH GCP, local regulatory requirements, and legal requirements,

including applicable privacy laws. They must be approved before use, as described in Appendix 10.1.1.

- The investigator, or his/her authorised representative, will provide the legal guardian with the written ICF and the participant with the assent form, if applicable. They must be informed that participation is voluntary. The legal guardian will be required to sign written consent, and the participant, if applicable, will be required to sign written assent after the nature of the study has been fully explained and before performance of any study-related activity.
- Assent requirements for paediatric participants may vary across regions and countries; local regulations should be followed as appropriate.
- The medical record must include a statement that written informed consent from the legal guardian and assent from the paediatric participant (if deemed appropriate by local ethics review or local regulations) were obtained before the participant was enrolled in the study and the date the written consent and assent were obtained. The medical record should describe how the investigator determined that the person signing the ICF was the participant's legal guardian. The authorised person obtaining the informed consent must also sign the ICF and assent form attesting that the paediatric participant did not show signs of dissent particularly in those studies including toddlers and small children; it should be written in language appropriate to the child's developmental and functional status.
- Minor participants who assent to a study and later withdraw that assent should not be maintained in the study against their will, even if their legal guardian still wants them to participate.
- A copy of the informed consent and assent forms must be provided to the participant and the participant's legal guardian.
- As appropriate, participants may be given the opportunity to meet privately with a member of the study site staff to ask confidential questions and to decline assent for confidential reasons which at their request, would not be shared with their legal guardian, unless required by local law.
- If an ICF amendment is not applicable to all participants, this will be communicated to the IEC/IRB with a rationale. A participant and the legal guardian must be re-consented and re-assented to the most current version of the ICF(s) during their participation in the study if the change has an impact on this participant.

